X303e	All	Proctocolitis
J41y.	All	Other idiopathic proctocolitis

J41yz	All	Other idiopathic proctocolitis NOS
J41z.	All	Idiopathic proctocolitis NOS
X304F	All	Caecitis
SNOMED Code	Term ID	Description
24526004		Inflammatory bowel disease (disorder)
721686000		Inflammatory polyps co-occurrent and due to inflammatory bowel disease (disorder)
6382002		Chronic inflammatory small bowel disease (disorder)
771333006		Immune dysregulation, inflammatory bowel disease, arthritis, recurrent infection syndrome (disorder)
128999004		Inflammatory disorder of digestive tract (disorder)
64226004		Colitis
54597004		Chronic colitis (disorder)
369445005		Chronic proctocolitis (disorder)
369447002		Chronic proctocolitis, confluent (disorder)
369446006		Chronic proctocolitis, patchy (disorder)
52506002		Chronic ulcerative rectosigmoiditis (disorder)
373639002		Distal colitis (disorder)
51290000		Diversion colitis (disorder)
29120000		Eosinophilic colitis (disorder)
783185002		Focal active colitis (disorder)
359660000		Idiopathic colitis (disorder)
235746007		Indeterminate colitis (disorder)
43752006		Inflammation of small intestine and colon (disorder)
13470001		Chronic ulcerative ileocolitis (disorder)
71207007		Noninfectious enteritis (disorder)
735731005		Chronic non-infectious enteritis of uncertain etiology (disorder)
307418008		Non-infective enteritis and colitis (disorder)
14066009		Noninfectious colitis (disorder)

414155001		Exacerbation of non-infective colitis (disorder)
53372009		Noninfectious sigmoiditis (disorder)
788718000		Iritis co-occurrent with inflammatory bowel disease (disorder)
64613007		Inflammation of small intestine (disorder)
52457000		Ileitis (disorder)
51151007		Noninfectious ileitis (disorder)
196983007		Regional ileocolitis (disorder)
302168000		Inflammation of large intestine (disorder)
3951002		Proctitis (disorder)
313327004		Inflammatory cloacogenic polyp (disorder)
28536002		Toxic megacolon (disorder)

sTable 1.2 WHO International Statistical Classification of Diseases (ICD-10) to be used to codes to be used to identify cases of IBD and IBD subtypes

Clinical entity	ICD 10 code	Definition
Crohn's disease	K50	Any diagnostic or indicative code for Crohn's disease, excluding ulcerative colitis
Ulcerative colitis	K51	Any diagnostic or indicative code for ulcerative colitis

Appendix 2

sTable 2.1 Read and SNOMED codes to be used to identify mental health conditions

Depressive episode		
Read V2 Code	Term ID	Description
E112.	All	Single major depressive episode
E1120	All	Single major depressive episode, unspecified
E1121	All	Single major depressive episode, mild
E1122	All	Single major depressive episode, moderate
E1123	All	Single major depressive episode, severe, without mention of psychosis
E1124	All	Single major depressive episode, severe, with psychosis
E1125	All	Single major depressive episode, in partial or unspecified remission
E1126	All	Single major depressive episode, in full remission
E112z	All	Single major depressive episode NOS
E113.	All	Recurrent major depressive episode
E1130	All	Recurrent major depressive episodes, unspecified
E1131	All	Recurrent major depressive episodes, mild
E1132	All	Recurrent major depressive episodes, moderate
E1133	All	Recurrent major depressive episodes, severe, without mention of psychosis
E1134	All	Recurrent major depressive episodes, severe, with psychosis
E1137	All	Recurrent depression
E113z	All	Recurrent major depressive episode NOS
E118.	All	Seasonal affective disorder
E11y2	All	Atypical depressive disorder

E11z2	All	Masked depression
E130.	All	Reactive depressive psychosis
E135.	All	Agitated depression
E2003	All	Anxiety with depression
E291.	All	Prolonged depressive reaction
E2B..	All	Depressive disorder NEC
E2B1.	All	Chronic depression
E2B0.	All	Postviral depression
Eu204	All	[X]Post-schizophrenic depression
Eu251	All	[X]Schizoaffective disorder, depressive type
Eu32.	All	[X]Depressive episode
Eu320	All	[X]Mild depressive episode
Eu321	All	[X]Moderate depressive episode
Eu322	All	[X]Severe depressive episode without psychotic symptoms
Eu323	All	[X]Severe depressive episode with psychotic symptoms
Eu324	All	[X]Mild depression
Eu325	All	[X]Major depression, mild
Eu326	All	[X]Major depression, moderately severe
Eu327	All	[X]Major depression, severe without psychotic symptoms
Eu328	All	[X]Major depression, severe with psychotic symptoms
Eu32y	All	[X]Other depressive episodes
Eu32z	All	[X]Depressive episode, unspecified
Eu33.	All	[X]Recurrent depressive disorder
Eu330	All	[X]Recurrent depressive disorder, current episode mild
Eu331	All	[X]Recurrent depressive disorder, current episode moderate

Eu332	All	[X]Recurrent depressive disorder, current episode severe without psychotic symptoms
Eu333	All	[X]Recurrent depressive disorder, current episode severe with psychotic symptoms
Eu334	All	[X]Recurrent depressive disorder, currently in remission
Eu33y	All	[X]Other recurrent depressive disorders
Eu33z	All	[X]Recurrent depressive disorder, unspecified
Eu412	All	[X]Mixed anxiety and depressive disorder
Read CTV3 Code	Term ID	Description
X00Sb	All	Mixed anxiety and depressive disorder
X00SO	All	Depressive disorder
X761L	All	Seasonal affective disorder
Xa0wV	All	Recurrent brief depressive disorder
X00SQ	All	Agitated depression
XE1YC	All	Reactive depression
X00SR	All	Endogenous depression
X00SS	All	Endogenous depression first episode
XE1Y0	All	Single major depressive episode
E1120	All	Single major depressive episode, unspecified
E1121	All	Single major depressive episode, mild
E1122	All	Single major depressive episode, moderate
E1123	All	Single major depressive episode, severe, without mention of psychosis
E1124	All	Single major depressive episode, severe, with psychosis
XaX53	All	Single major depressive episode, severe, with psychosis, psychosis in remission
E1125	All	Single major depressive episode, in partial or unspecified remission
E1126	All	Single major depressive episode, in full remission
E112z	All	Single major depressive episode NOS

XM1GC	All	Endogenous depression - recurrent
E1130	All	Recurrent major depressive episodes, unspecified
E1131	All	Recurrent major depressive episodes, mild
E1132	All	Recurrent major depressive episodes, moderate
E1133	All	Recurrent major depressive episodes, severe, without mention of psychosis
E1134	All	Recurrent major depressive episodes, severe, with psychosis
E1135	All	Recurrent major depressive episodes, in partial or unspecified remission
E1136	All	Recurrent major depressive episodes, in full remission
E113z	All	Recurrent major depressive episode NOS
X00SU	All	Masked depression
E11y2	All	Atypical depressive disorder
X00S8	All	Post-schizophrenic depression
XSEGJ	All	Major depressive disorder
XSKr7	All	Cotard syndrome
XSGol	All	Moderate major depression
XSGok	All	Mild major depression
XSGom	All	Severe major depression without psychotic features
XSGon	All	Severe major depression with psychotic features
E1137	All	Recurrent depression
E130.	All	Reactive depressive psychosis
E2B..	All	Depressive disorder NEC
E2B0.	All	Postviral depression
E2B1.	All	Chronic depression
Eu320	All	[X]Mild depressive episode
Eu321	All	[X]Moderate depressive episode
Eu331	All	[X]Recurrent depressive disorder, current episode moderate

XE1Y1	All	Recurrent major depressive episodes
XE1ZY	All	[X]Severe depressive episode without psychotic symptoms
XE1ZZ	All	[X]Severe depressive episode with psychotic symptoms
XE1Za	All	[X]Other depressive episodes
XE1Zb	All	[X]Depressive episode, unspecified
XE1Zd	All	[X]Recurrent depressive disorder, current episode severe without psychotic symptoms
XE1Ze	All	[X]Recurrent depressive disorder, current episode severe with psychotic symptoms
XE1Zf	All	[X]Recurrent depressive disorder, unspecified
XaB9J	All	Depression NOS
XaCHr	All	[X] Single episode agitated depression without psychotic symptoms
XaCHs	All	[X] Single episode major depression without psychotic symptoms
XaCIs	All	Mild depression
XaCIt	All	Moderate depression
XaCIu	All	Severe depression
SNOMED Code	Term ID	Description
832007'		Moderate major depression (disorder)
2618002'		Chronic recurrent major depressive disorder (disorder)
14070001'		Multi-infarct dementia with depression (disorder)
14183003'		Chronic major depressive disorder, single episode (disorder)
15193003'		Severe recurrent major depression with psychotic features, mood-incongruent (disorder)
15639000'		Moderate major depression, single episode (disorder)
18818009'		Moderate recurrent major depression (disorder)
19527009'		Single episode of major depression in full remission (disorder)

20250007'		Severe major depression, single episode, with psychotic features, mood-incongruent (disorder)
25922000'		Major depressive disorder, single episode with postpartum onset (disorder)
28475009'		Severe recurrent major depression with psychotic features (disorder)
30605009'		Major depression in partial remission (disorder)
33078009'		Severe recurrent major depression with psychotic features, mood-congruent (disorder)
33135002'		Recurrent major depression in partial remission (disorder)
33736005'		Severe major depression with psychotic features, mood-congruent (disorder)
35489007'		Depressive disorder (disorder)
36474008'		Severe recurrent major depression without psychotic features (disorder)
36923009'		Major depression, single episode (disorder)
38694004'		Recurrent major depressive disorder with atypical features (disorder)
39809009'		Recurrent major depressive disorder with catatonic features (disorder)
40379007'		Mild recurrent major depression (disorder)
40568001'		Recurrent brief depressive disorder (disorder)
42925002'		Major depressive disorder, single episode with atypical features (disorder)
48589009'		Minor depressive disorder (disorder)
58703003'		Postpartum depression (disorder)
60099002'		Severe major depression with psychotic features, mood-incongruent (disorder)
66344007'		Recurrent major depression (disorder)
69392006'		Major depressive disorder, single episode with catatonic features (disorder)
70747007'		Major depression single episode, in partial remission (disorder)
71336009'		Recurrent major depressive disorder with postpartum onset (disorder)
73867007'		Severe major depression with psychotic features (disorder)
75084000'		Severe major depression without psychotic features (disorder)
76441001'		Severe major depression, single episode, without psychotic features (disorder)

77911002'		Severe major depression, single episode, with psychotic features, mood-congruent (disorder)
79298009'		Mild major depression, single episode (disorder)
79842004'		Stuporous depression (disorder)
82218004'		Postoperative depression (disorder)
83458005'		Agitated depression (disorder)
87414006'		Reactive depression (situational) (disorder)
87512008'		Mild major depression (disorder)
161469008'		History of depression (situation)
191466007'		Arteriosclerotic dementia with depression (disorder)
191495003'		Drug-induced depressive state (disorder)
191604000'		Single major depressive episode, severe, with psychosis (disorder)
191610000'		Recurrent major depressive episodes, mild (disorder)
191611001'		Recurrent major depressive episodes, moderate (disorder)
191613003'		Recurrent major depressive episodes, severe, with psychosis (disorder)
191616006'		Recurrent depression (disorder)
191659001'		Atypical depressive disorder (disorder)
191676002'		Reactive depressive psychosis (disorder)
192046006'		Brief depressive adjustment reaction (disorder)
192049004'		Prolonged depressive adjustment reaction (disorder)
192079006'		Postviral depression (disorder)
192080009'		Chronic depression (disorder)
231485007'		Post-schizophrenic depression (disorder)
231499006'		Endogenous depression first episode (disorder)
231500002'		Masked depression (disorder)
231504006'		Mixed anxiety and depressive disorder (disorder)

237349002'		Mild postnatal depression (disorder)
237350002'		Severe postnatal depression (disorder)
237739002'		Pseudo-Cushing's syndrome of depression (disorder)
247803002'		Seasonal affective disorder (disorder)
268621008'		Recurrent major depressive episodes (disorder)
272022009'		Complaining of feeling depressed (finding)
274948002'		Endogenous depression - recurrent (disorder)
300706003'		Endogenous depression (disorder)
310495003'		Mild depression (disorder)
310496002'		Moderate depression (disorder)
310497006'		Severe depression (disorder)
319768000'		Recurrent major depressive disorder with melancholic features (disorder)
320751009'		Major depression, melancholic type (disorder)
321717001'		Involutional depression (disorder)
366979004'		Depressed mood (finding)
370143000'		Major depressive disorder (disorder)
394924000'		Symptoms of depression (finding)
395072006'		Counseling for postnatal depression (procedure)
430852001'		Severe major depression, single episode, with psychotic features (disorder)
450714000'		Severe major depression (disorder)
704678007'		Depressed mood with postpartum onset (finding)
712823008'		Acute depression (disorder)
718636001'		Minimal depression (disorder)
719592004'		Moderately severe major depression (disorder)
719593009'		Moderately severe depression (disorder)
720451004'		Minimal recurrent major depression (disorder)

720452006'		Moderately severe recurrent major depression (disorder)
720453001'		Moderately severe major depression single episode (disorder)
720454007'		Minimal major depression single episode (disorder)
720455008'		Minimal major depression (disorder)
723928009'		Mood disorder with depressive symptoms caused by alcohol (disorder)
723930006'		Mood disorder with mixed manic and depressive symptoms caused by alcohol (disorder)
724676000'		Mood disorder with depressive symptoms caused by sedative (disorder)
724677009'		Mood disorder with depressive symptoms caused by hypnotic (disorder)
724678004'		Mood disorder with depressive symptoms caused by anxiolytic (disorder)
724690002'		Mood disorder with depressive symptoms caused by cocaine (disorder)
724757005'		Depressive symptoms due to primary psychotic disorder (disorder)
726772006'		Major depression with psychotic features (disorder)
762321000'		Mood disorder with depressive symptoms caused by opioid (disorder)
762329003'		Mood disorder with depressive symptoms caused by stimulant (disorder)
762336002'		Mood disorder with depressive symptoms caused by hallucinogen (disorder)
762339009'		Mood disorder with depressive symptoms caused by volatile inhalant (disorder)
762512002'		Mood disorder with depressive symptoms caused by synthetic cathinone (disorder)
768835002'		Depression care management (procedure)
788120007'		Antenatal depression (disorder)
838529004'		Mood disorder with mixed depressive and manic symptoms caused by amfetamine and amfetamine derivative (disorder)
871840004'		Episode of depression (finding)

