Furthering our understanding of the psychosocial sequelae of IBD in children and young adults is particularly important in light of evidence suggesting that symptoms of anxiety and depression may decrease adherence to treatment, thus impacting on longer term disease outcomes,(6) and has been emphasized in a recent call to action issued within gastroenterology to improve understanding and early identification of comorbidities associated with IBD.(10)

To the best of our knowledge, there have not been any large population-based studies assessing the association between psychosocial comorbidities in IBD in

children and young adults and disease related outcomes. The aim of this study is therefore to fill this data gap, and to examine the following objectives.

Such new insights will be valuable for clinicians in optimising patient care for IBD patients; allowing early interventions to be targeted to those most at risk, and potentially preventing the development of more serious mental health problems such as depression; linked to difficulties with medication adherence, and anxiety; which may exacerbate future disease activity.(7, 10)

Ultimately, we anticipate that these data will be useful in understanding the potential cycle and interrelationship between IBD and mental health in children and young adults.

Objectives: Stream 1 – Incidence of mental health conditions

Primary Objectives

- Compare the risk and cumulative incidence of mental health conditions in children and young adults with IBD compared to matched population controls in the primary care setting, stratified by IBD type

Secondary Objectives

- Determine severity of mental health conditions in those with and without IBD (e.g. evidence of self-harm, suicide attempt, behavioural disorders)

Objectives: Stream 2 – Impacts of mental health conditions

Primary Objective:

- Determine the association of mental health conditions in children and young adults with IBD on quality-of-life indicators

Secondary Objectives:

- Compare IBD severity/disease markers in children and young adults with IBD with and without mental health illness

- Compare healthcare resource utilisation in children and young adults with IBD with and without mental health illness

Methods

The study protocol was specified a priori and registered with ClinicalTrials.gov (Study identifier: NCT05206734).

Data source

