The Optimum Patient Care Research Database (OPCRD). This database incorporates pseudonymised primary care records from 700 GP practices distributed across England, Wales, Scotland and Northern Ireland. The current OPCRD cohort size is over 5 million actively registered people, and historic records available for 10.1 million people. The cohort dataset can be enhanced through direct-to-patient and direct-to-care provider questionnaires at additional cost if required.

Study design

The proposed study will use the retrospectively collected data of all eligible patients within the database at the date of data extraction. Within this primary care cohort, all patients with IBD comprising of the three main subtypes; ulcerative colitis (UC), Crohn's disease (CD) and IBD unclassified (IBDU), excluding microscopic colitis, radiation induced enterocolitis and drug-induced enterocolitis, will be identified using diagnostic codes and prescription records. A diagnostic algorithm will be developed to facilitate robust case identification of IBD and IBD subtypes, as well as mental health outcomes.

Statistical methods

We will use standard descriptive statistics (mean, standard deviations, etc) to describe the characteristics of the study cohort.

Recorded sociodemographic characteristics and clinical features

Sociodemographic data will comprise by age group, age at diagnosis, gender, ethnicity, and socioeconomic status. Ethnicity will be categorised as follows to be consistent with the UK official census categories: White, Asian, Black African/Caribbean, Mixed, and Other. The index of multiple deprivation (IMD) will be used as a measure of socioeconomic status. This is derived from patient postcode at the point of data extraction.

Stream 1: Study Cohort

Stream 1: Definition of people with new onset IBD

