The eligible PIBD cases will comprise all incident cases of PIBD over the last decade, we will not follow patients up beyond 01/01/2020 due to changes in patient health behaviour and primary care interactions due to COVID-19. We will extract sociodemographic details for all these cases and matched controls (described below). Sociodemographic data will comprise by age group, gender, ethnicity, and socioeconomic status. Ethnicity will be categorised as follows to be consistent with the UK official census categories: White, Asian, Black African/Caribbean, Mixed, and Other. The index of multiple deprivation (IMD) will be used as a measure of socioeconomic status. This is derived from patient postcode at the point of data extraction.

Stream 1: Definition of matched controls without IBD

We will match each incident case of PIBD with controls (children without IBD) using propensity score matching (matching on the sociodemographic variables list above and matching within primary care practice if numbers allow). People with a known diagnosis of irritable bowel syndrome (IBS) will be excluded from the potential pool of controls. We will compare the incidence of new onset mental health conditions in PIBD and controls using a similar approach to that used by Butwick et al. (2019) in their paper exploring psychiatric disorders in a

PIBD cohort in Sweden.(9) The mental health conditions to be examined are listed in table 1 although there is scope to add to or modify these in discussion with the study authors. For a composite 'any psychological condition' outcome (see Table 1), risk will be stratified by age of PIBD onset and sex.

We will then go beyond the analysis of the Swedish study to estimate the cumulative risk of the 'any psychological condition' composite outcome in PIBD patients compared with controls. This will provide a unique, robust, estimate of the overall mental health burden (prevalence) in PIBD.

Condition	Description
Primary outcomes	
Any psychological condition	A composite of all the chronic psychiatric conditions listed below* (depression, anxiety, eating disorders, body image disorder, attention-deficit disorder, behavioural disorders, adjustment disorder, acute stress disorder, and post-traumatic stress disorder)
Depression	Major recurrent depression or treated depressive episode
Anxiety	Non-phobia related anxiety episodes or disorder
Secondary outcomes	
Self-harm	Any coded episode of deliberate self-harm of any type

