
Appendices

Appendix 1

sTable 1.1. Read and SNOMED codes to be used to identify cases of IBD and IBD subtypes

Ulcerative Colitis (UC)		
Read V2 Code	Term ID	Description
J41..	All	Ulcerative colitis and/or proctitis
J410.	All	Ulcerative proctocolitis
J4100	All	Ulcerative ileocolitis
J4101	All	Ulcerative colitis
J4102	All	Ulcerative rectosigmoiditis
J4103	All	Ulcerative proctitis
J4104	All	Exacerbation of ulcerative colitis
J410z	All	Ulcerative proctocolitis NOS
J411.	All	Ulcerative (chronic) enterocolitis
J412.	All	Ulcerative (chronic) ileocolitis
J413.	All	Ulcerative pancolitis
N0454	All	Juvenile arthritis in ulcerative colitis
N0310	All	Arthropathy in ulcerative colitis
Read CTV3 Code	Term ID	Description
XE0ag	All	Ulcerative colitis
XaZ2j	All	Left sided ulcerative colitis
XaYzX	All	Ulcerative pancolitis

XaK6E	All	Exacerbation of ulcerative colitis
J410.	All	Ulcerative proctocolitis
J4100	All	Ulcerative ileocolitis
J410z	All	Ulcerative proctocolitis NOS
J4103	Y30D7	Ulcerative proctitis
Jyu41	All	[X]Other ulcerative colitis
SNOMED Code	Term ID	Description
13470001		Chronic ulcerative ileocolitis (disorder)
14311001		Severe chronic ulcerative colitis (disorder)
15342002		Chronic ulcerative enterocolitis (disorder)
24829000		Eosinophilic ulcerative colitis (disorder)
43752006		Ulcerative colitis and/or proctitis
52231000		Chronic ulcerative proctitis (disorder)
52506002		Chronic ulcerative rectosigmoiditis (disorder)
64766004		Ulcerative colitis (disorder)
78324009		Mild chronic ulcerative colitis (disorder)
78712000		Moderate chronic ulcerative colitis (disorder)
128600008		Acute ulcerative colitis (disorder)
155764007		Ulcerative colitis
196986004		Ulcerative proctocolitis
196987008		Ulcerative ileocolitis
196988003		Ulcerative colitis
196989006		Ulcerative proctocolitis
196990002		Ulcerative proctocolitis NOS
196991003		Ulcerative enterocolitis
196992005		Ulcerative ileocolitis
197535008		[X]Other ulcerative colitis
201727001		Arthropathy in ulcerative colitis (disorder)

201807008		Juvenile arthritis in ulcerative colitis (disorder)
235714007		Ulcerative enterocolitis (disorder)
266447004		Ulcerative colitis
275549008		History of ulcerative colitis (situation)
295046003		Ulcerative proctocolitis (disorder)

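### Three SNOMED codes sit in both the UC and the IBDU lists, and the by-type comparison in the Stream 1 primary objective is not carried into the methods

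*Combined protocol and SAP*

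**What the plan says.** All references are to the combined protocol and SAP.

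Objectives: Stream 1, Primary Objectives, sets out a comparison of the risk and cumulative incidence of mental health conditions in IBD "compared to matched population controls in the primary care setting, stratified by IBD type". The Study design section names three types, UC, CD and IBDU, and leaves their assignment to later work: "A diagnostic algorithm will be developed to facilitate robust case identification of IBD and IBD subtypes".

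Appendix 1, sTable 1.1 gives the code lists for each type. Its UC SNOMED list includes "Ulcerative colitis and/or proctitis", "Chronic ulcerative rectosigmoiditis (disorder" and "Chronic ulcerative ileocolitis (disorder". The last two descriptions appear again, under the same numbers, in the IBDU SNOMED list. The number attached to the first also appears again there, but is now described as "Inflammation of small intestine and colon (disorder".

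The only stratification of the case-versus-control comparison in the Stream 1 methods is for the composite outcome, where "risk will be stratified by age of PIBD onset and sex".

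**The concern.** An estimate stratified by type needs types that are defined so that each patient falls into one of them. As listed, a patient whose only IBD code is one of the three shared codes meets the definition of both UC and IBDU. Two of the codes name ulcerative disease, so UC patients could be counted in the group meant for disease that cannot be classified. The third code has two incompatible meanings, so some patients will be typed on a wrong description whichever list is followed.

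The second part is a gap between objective and methods. If no by-type estimate is specified in advance, any by-type result reported later has no agreed model, control set or outcome list behind it, although the Methods section describes the protocol as set a priori. The by-type part of the primary objective is at stake, and mainly the UC-versus-IBDU boundary.

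**Working it through.** The documents state no sample size, event count or power for this point, so there is no planned figure to reproduce. The check is a comparison of lists, followed by a reading of the Stream 1 methods.

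**1. Overlap between lists.** Inputs: the UC, CD and IBDU lists in sTable 1.1, taken separately for each coding system. No SNOMED, Read V2 or CTV3 code is repeated within its own list.

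| System | UC codes | CD codes | IBDU codes | UC and IBDU | UC and CD | CD and IBDU |
|---|---|---|---|---|---|---|
| SNOMED | 56 | 74 | 34 | 3 | 0 | 0 |
| Read V2 | 13 | 14 | 15 | 0 | 0 | 0 |
| Read CTV3 | 9 | 19 | 23 | 0 | 0 | 0 |

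Shared share of the SNOMED lists: 3/56 = 5.4% of UC codes and 3/34 = 8.8% of IBDU codes. These are shares of codes, not of patients. The documents give no code frequencies, so a patient count does not follow.

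**2. The three shared codes.**

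| SNOMED code | Description under UC | Description under IBDU |
|---|---|---|
| 13470001 | "Chronic ulcerative ileocolitis (disorder" | the same |
| 52506002 | "Chronic ulcerative rectosigmoiditis (disorder" | the same |
| 43752006 | "Ulcerative colitis and/or proctitis" | "Inflammation of small intestine and colon (disorder" |

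The protocol's own Read V2 lists place ulcerative ileocolitis (J4100, J412.) and ulcerative rectosigmoiditis (J4102) under UC only. The first two SNOMED codes therefore conflict with the plan's own handling of the same diagnoses. For 43752006, one number cannot mean both things. The documents do not show which row is wrong.

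**3. Is there a rule that resolves the overlap?** The Study design text promises an algorithm but gives no order of precedence. In sTable 1.2 (ICD-10) there is a CD row that excludes UC, a UC row with no exclusion, and no IBDU row. Neither place settles a UC/IBDU conflict.

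**4. Lists after a repair.** Removing 13470001 and 52506002 from IBDU leaves 34 - 2 = 32 IBDU codes. If 43752006 then stays under UC only, the lists are UC 56 and IBDU 32 - 1 = 31. If it stays under IBDU only, they are UC 56 - 1 = 55 and IBDU 32. Either way the overlap is zero and CD remains at 74.

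**5. Stream 1 analyses by type.**

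| Analysis in Stream 1 | Groups or factors | By IBD type? |
|---|---|---|
| Stratified risk of the composite | onset age, sex | No |
| Within-cohort associations | onset age, sex, ethnicity, deprivation | No |
| Cox models, cases versus controls | all cases pooled; IBD type not among the covariates | No |
| Cumulative risk plots | all cases versus controls | No |
| Sensitivity analysis | controls with a recent consultation | No |

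By-type analyses specified: 0 of 5.

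**The case against.** The strongest reply is that the algorithm is still to come and can resolve the overlap without touching the lists. A rule that classes a patient as IBDU only when no UC or CD code is present would send all three shared codes to UC. That is correct. A reader might infer that any algorithm built on these lists must produce overlapping strata, and the documents do not support that. Two things survive the reply. No such rule is written, and the rule cannot repair 43752006: it would class those patients as UC even if the IBDU description proves to be the right one.

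On the methods, the objective itself commits to stratification by type, and the sentence on onset age and sex does not say that these are the only strata. So the by-type analysis is unspecified, not ruled out. A reader might also infer that the plan fails to compare the types with one another. The objective does not ask for that. It asks for IBD against controls within each type.

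Finally, a reader might infer that misplaced UC patients swamp the IBDU group, or that the headline result is biased. The first needs code frequencies and a case mix that the documents do not give. The second does not follow, because all three codes count as IBD in either list and the pooled comparison uses every type together.

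**Conclusion.** The point holds in a limited form. The code lists are wrong as written at three places, for strata that the primary objective relies on, and the objective's by-type element has no matching analysis. Both can be confirmed from the documents alone.

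The effect is confined to the UC/IBDU boundary in SNOMED-coded records. CD and both Read lists are clean. The pooled estimates are untouched, on the assumption that both descriptions of 43752006 belong in the IBD case definition, as the lists treat them. The impact on the by-type results could be negligible or material, and confidence on that is low. It is worth correcting before data extraction, whose date the Stream 1 methods still leave open, but it is not a threat to the main finding.

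**What to change.** 1. Delete 52506002 and 13470001 from the IBDU SNOMED list.
2. Check 43752006 against the terminology, correct the wrong row, and keep the code in one list only.
3. State a fixed precedence for type, using only codes recorded up to the index date: IBDU only if there is no UC or CD code. Say also how a patient with both UC and CD codes is classed. Later codes should not be used, because follow-up starts at diagnosis and the stratum would then depend on information gathered during follow-up.
4. Add to the Stream 1 methods adjusted hazard ratios and cumulative incidence for UC, CD and IBDU, each against its own matched controls, for the primary outcomes. Otherwise, remove the type stratification from the objective.

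Cost: a code-list edit, one check against the terminology, and a short paragraph of text. If the analyses are added, three primary outcomes (any psychological condition, depression, anxiety) by three types gives 3 x 3 = 9 further hazard ratios, plus cumulative incidence curves by type. The IBDU estimates may be imprecise, and the text should say so in advance. No new data are needed.
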